# Secondary Objectives:

- To compare the long-term (6-month follow-up) clinical outcomes and healthcare utilization based on status on the CPR and the treatment received. The investigators hypothesize that patients who are positive on the CPR and receive TJM will demonstrate improved disability and lower health care utilization than patients who are negative on the CPR and receive TJM and compared to patients who are positive on the CPR but receive an alternative exercise program without TJM.
- 2. Compare changes in pain and fear-avoidance beliefs at long-term follow-up (6-month follow-up) based on status on the CPR and the treatment received. The investigators hypothesize that patients who are positive on the CPR and receive TJM will achieve greater improvement in 6-month pain levels and a reduction in fear-avoidance beliefs compared to patients who are negative on the CPR and receive TJM and compared to patients who are positive on the CPR but receive an alternative exercise program without TJM.

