Numeric Pain Rating Scale and Pain Diagram: An 11-point NPRS will be used to measure pain intensity. The scale is anchored on the left with the phrase "No Pain" and on the right with the phrase "Worst Imaginable Pain". Numeric pain scales have been shown to be reliable and valid.  Patients rate their current level of pain and their worst and least amount of pain in the last 24 hours. The average of the three ratings or any single rating may be used to represent the patient's level of pain. The pain diagram is used to record the location and nature of a patient's neck symptoms by drawing it on a human figure. This information will be used to determine whether the patient meets the study inclusion criteria. The pain diagram has shown to be a reliable tool to localize a patient's symptoms. (See Appendix B)

Modified Fear-Avoidance Beliefs Questionnaire (FABQ): The modified FABQ is a 16-item questionnaire designed to quantify fear and avoidance beliefs in patients with LBP. The FABQ has two sub-scales, a 7-item scale to measure fear-avoidance beliefs about work and a 4-item scale to measure fear-avoidance beliefs about work and a 4-item scale to scores ranging between 0-24 and 0-42 for the physical activity and work subscales, respectively, with higher scores representing increased fear-avoidance beliefs. (See Appendix C)

Patient Global Rating of Change (GROC): The fifteen-point global rating scale described by Jaeschke et al, will be used. The scale ranges from –7 (a very great deal worse) to zero (about the same) to +7 (a very great deal better). Intermittent descriptors of worsening or improving are assigned values from –1 to –6 and +1 to +6 respectively. The global rating will be administered at the follow-up examinations only. (See Appendix D)

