Specific Aims: Primary Aim #1: To determine the validity of the clinical prediction rule for identifying patients with neck pain who are likely to benefit from C-TJM. Pain and Disability. The investigators will examine the primary aim with separate random intercept linear mixed models with treatment group (MTE vs. MoE), status on the CPR (positive or negative) and time (baseline, 1-week and 4weeks) as fixed effects. The dependent variables will be pain (NPRS) and disability (NDI score). The hypothesis of interest is the group \* CPR status \* time interaction. The primary dependent variables are the 1-week NPRS and NDI scores to mirror the follow-up used in Cleland and colleagues' study. The investigators will assess the NPRS and NDI scores after 4 weeks to determine whether a patient's status on the rule predicts outcome at a longer follow-up. The investigators will perform planned pairwise comparisons at each follow-up period by using the Bonferroni test of inequality. The investigators hypothesize that patients who are positive on the rule and receive TJM will achieve greater improvement in immediate (1-week) and 4-week pain and disability, than patients who are negative on the rule and receive TJM, and compared to patients who are positive on the rule but receive an alternative exercise program without TJM. Because the rule is believed to be specific to a TJM intervention, investigators hypothesize that outcomes among those receiving the MoE treatment would not differ on the basis of a patient's status on the rule.

Secondary Aim #1: To compare the long-term (6-month) pain and disability scores (clinical

outcomes) and healthcare utilization based on status on the clinical prediction rule and the treatment received. The investigators will examine this with random intercept linear mixed models with treatment group (MTE vs. MoE), status on the CPR (positive or negative), and time (baseline and 6-months) as fixed effects. The dependent variables will be pain (NPRS) and disability (NDI) scores. The investigators will perform planned pairwise comparisons at each follow-up period by using the Bonferroni test of inequality. The hypothesis of interest is the group \* status on CPR \* time interaction. The investigators hypothesize that patients who are positive on the rule and received TJM would experience greater improvement at 6-months than patients who are negative on the rule and received the MoE program without TJM.

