The investigators will also examine healthcare utilization using a two-way ANOVA comparing the number of healthcare visits post-treatment sessions with treatment group (MTE vs. MoE) and status on the clinical prediction rule (positive or negative) as independent variables. If appropriate, the interaction effect of the two independent variables will also be accounted for in the analysis. The dependent variable is the number of healthcare visits after completion of the treatment. The investigators hypothesize that patients who are positive on the rule and received TJM utilize less additional healthcare visits after completion of the treatment than patients who are negative on the rule and received the MoE program without TJM.

Secondary Aim #2: To compare changes in GROC and fear-avoidance beliefs at long-term follow-up (6-month) based on status on the clinical prediction rule and the treatment received. The investigators will examine this with separate random intercept linear mixed models with treatment group (MTE vs. MoE), status on the clinical prediction rule (positive or negative), and time (baseline and 6-months) as fixed effects. The dependent variables will be GROC changes and fear avoidance beliefs. The hypothesis of interest is the group \* status on CPR \* time interaction. The investigators will perform planned pairwise comparisons at each follow-up period by using the Bonferroni test of inequality. The investigators hypothesize that patients who are positive on the rule and received TJM would experience greater reduction in pain and fear avoidance beliefs than patients who are negative on the rule and received TJM, compared with patients who are positive on the rule but received the MoE program without TJM.

Missing Data. While analysis using mixed models allows all observed data to be included in the analysis under the assumption that the data are missing at random, if substantial missing data occurs, multiple imputation or mean conditional imputation will be used with subsequent sensitivity analyses to explore the impact of imputation on results. To address the issue of artificially reduced estimates of stochastic uncertainty produced by imputation, bootstrapping procedures will be used on the entire imputation and estimation process.

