#### Scoring the FABQ

The FABQ consists of 2 subscales, which are reflected in the division of the outcome form into 2 separate sections. The first subscale (items 1-5) is the Physical Activity subscale (FABQPA), and the second subscale (items 6-16) is the Work subscale (FABQW). Although we are only interested in the FABQW subscale for the purposes of classifying patients, all items should be completed. Interestingly, not all items contribute to the score for each subscale; however the patient should still complete all items as these items were included when the reliability and validity of the scale was initially established. Also note that there is no total score where each subscale score is added as each subscale exists as a separate entity. The method to score each subscale is outlined below. (Note: It is extremely important to ensure all items are completed as there is no procedure to adjust for incomplete items.)

Scoring the Physical Activity subscale (FABQPA)

1. Sum items 2, 3, 4, and 5 (the score circled by the patient for these items).

2. Record this total on the form.

Scoring the Work subscale (FABQW) 1. Sum items 6, 7, 9, 10, 11, 12, and 15. 2. Record this total on the form.

Waddell et al: FABQ; Pain. 1993; 52: 157-68.

FABQPA (2,3,4,5): \_\_\_\_/24

FABQW (6,7,9,10,11,12,15): /42

T

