#### Appendix G: Administration of Questionnaires

The investigators will use the following questionnaires in their entirety as noted in the prior appendices.

Baseline Examination/Visit 1:

- Informed consent
- Demographic Information (Appendix E)
- Neck Disability Index (Appendix A)
- Fear Avoidance and Beliefs Questionnaire (Appendix C)
- Numeric Pain Rating Scale and Pain Diagram (Appendix B)

Visit 2:

• Global Rating of Change Scale (Appendix D)

1 Week Follow-Up Timepoint/Visit 3:

- Global Rating of Change Scale (Appendix D)
- Neck Disability Index (Appendix A)
- Fear Avoidance and Beliefs Questionnaire (Appendix C)
- Numeric Pain Rating Scale and Pain Diagram (Appendix B)

Visit 4:

• Global Rating of Change Scale (Appendix D)

Visit 5:

• Global Rating of Change Scale (Appendix D)

1 Month Follow-Up Timepoint:

- Global Rating of Change Scale (Appendix D)
- Neck Disability Index (Appendix A)
- Fear Avoidance and Beliefs Questionnaire (Appendix C)
- Numeric Pain Rating Scale and Pain Diagram (Appendix B)

3 Month Follow-Up Timepoint:

- Global Rating of Change Scale (Appendix D)
- Neck Disability Index (Appendix A)
- Fear Avoidance and Beliefs Questionnaire (Appendix C)
- Numeric Pain Rating Scale and Pain Diagram (Appendix B)

6 Month Follow-Up Timepoint:

- Global Rating of Change Scale (Appendix D)
- Neck Disability Index (Appendix A)
- Fear Avoidance and Beliefs Questionnaire (Appendix C)

• Numeric Pain Rating Scale and Pain Diagram (Appendix B)

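### Three secondary-analysis statements in section 7.0 need rewording: the 6-month GROC test relies on a baseline that is not collected, the healthcare-visit interaction is optional, and the Secondary Aim #1 comparator contradicts the objective

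*Combined protocol and SAP*

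**What the plan says.** **GROC.** In section 7.0, Secondary Aim #2 specifies random-intercept mixed models with treatment group, CPR status "and time (baseline and 6-months) as fixed effects. The dependent variables will be GROC changes and fear avoidance beliefs". What it sets out to test is the three-way interaction of treatment, CPR status and time. On collection, section 4.0 states: "The global rating will be administered at the follow-up examinations only". The visit schedule in section 5.0 and Appendix G both start the GROC at Visit 2. Section 5.0 (treatment sessions 3 to 5) describes it as perceived recovery since the baseline examination. The fear-avoidance questionnaire (FABQ) is collected at baseline.

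**Healthcare visits.** Section 7.0 plans a two-way ANOVA of the number of post-treatment visits on treatment group and CPR status. On the interaction it says: "If appropriate, the interaction effect of the two independent variables will also be accounted for in the analysis". It gives no criterion for deciding.

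**Hypothesis sentences.** Section 2.0 (Secondary Objectives) compares CPR-positive patients given TJM with two groups: CPR-negative patients given TJM, and CPR-positive patients not given TJM. It does so for both disability and healthcare use. The Secondary Aim #1 sentences in section 7.0, one for 6-month pain and disability and one for visits, instead name a single comparator: CPR-negative patients in the mobilization plus exercise (MoE) arm.

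**The concern.** Each statement affects what can be concluded about the rule at 6 months.

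- The GROC test is named on a time factor with only one observed level, so the analyst must choose another model, and the plan does not say which.
- For visits, whether the four cell means are free to differ is left to judgement. If the interaction is dropped, the rule-status difference is forced to be equal in both arms. The primary-aim paragraph describes a different pattern: "Because the rule is believed to be specific to a TJM intervention, investigators hypothesize that outcomes among those receiving the MoE treatment would not differ" by rule status.
- The comparator in the Secondary Aim #1 sentences differs from the CPR-positive/TJM cell in both rule status and treatment. A difference there could come from prognosis, from treatment, or from both, and would still be reported as support for the hypothesis.

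**Working it through.** **The plan's own figure.** Section 7.0 gives one sample-size figure: 31 per cell for 1-week NDI change (difference 10, SD 12, two-sided alpha 0.05, 90% power). n = 2 × (1.960 + 1.282)² × 12²/10² = 2 × 10.51 × 1.44 = 30.3, rounded up to 31. It reproduces. The plan gives no figure for the secondary analyses, and nothing below changes this one.

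**GROC: can the term be estimated?** Code treatment g, CPR status c and time t as 0/1. The planned fixed-effect columns are 1, g, c, t, gc, gt, ct, gct.

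- With baseline and 6-month rows, as for FABQ, the rank is 8 of 8.
- With 6-month rows only, t = 1 throughout. Then t equals the intercept, gt = g, ct = c and gct = gc. Four distinct columns remain, so the rank is 4 of 8 and gct cannot be separated from gc.
- There is then one record per patient, so the random intercept has no role either.

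**Visits: what the additive model does.** Take equal cells, as planned, and suppose that only CPR+/TJM differs, by −4 visits (an illustrative value; results scale with it). The mean is −2 for CPR+ and 0 for CPR−, −2 for TJM and 0 for MoE, and −1 overall. Without the interaction, fitted cell = rule mean + treatment mean − overall mean.

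| Cell | True | Fitted |
|---|---|---|
| CPR+/TJM | −4 | −2 − 2 + 1 = −3 |
| CPR+/MoE | 0 | −2 + 0 + 1 = −1 |
| CPR−/TJM | 0 | 0 − 2 + 1 = −1 |
| CPR−/MoE | 0 | 0 + 0 + 1 = 1 |

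- CPR+/TJM minus CPR−/TJM: true −4, fitted −3 − (−1) = −2.
- CPR+/TJM minus CPR+/MoE: true −4, fitted −3 − (−1) = −2.
- CPR+/MoE minus CPR−/MoE: true 0, fitted −1 − 1 = −2.
- CPR+/TJM minus CPR−/MoE: true −4, fitted −3 − 1 = −4.

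If the truth were the additive pattern (−3, −1, −1, 1), the fitted cells would be identical. The additive model cannot tell a TJM-specific effect from two separate effects, and the stated CPR−/MoE comparison is −4 under both.

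**Comparators: weight on each effect.** With ±1 coding, the weights on (CPR status, treatment, interaction) are:

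- CPR+/TJM vs CPR−/MoE (section 7.0 sentences): (2, 2, 0)
- CPR+/TJM vs CPR−/TJM (section 2.0): (2, 0, 2)
- CPR+/TJM vs CPR+/MoE (section 2.0): (0, 2, 2)
- Difference in differences: (0, 0, 4)

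The section 7.0 comparator has zero weight on the interaction. Each section 2.0 contrast mixes the interaction with one main effect, so either can be non-zero when the interaction is zero.

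**Power of the interaction.** Two-sided 0.05, 80% power, 35 per cell before dropout, in SD units:

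- Difference in differences: (1.960 + 0.842) × 2/√35 = 2.802 × 0.338 = 0.95 SD.
- One pairwise contrast: 2.802 × √(2/35) = 2.802 × 0.239 = 0.67 SD, before any Bonferroni adjustment.

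**The case against.** The case for leaving the text alone has real force.

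- **GROC.** The plan writes of GROC changes, and the rating already is a change. With no baseline rows the time terms drop out, leaving treatment, CPR status and their interaction at 6 months, which is the model recommended below. This stands as a limit on the harm. It does not make the named test estimable.
- **Visits.** A reader might infer that the interaction is the only test that addresses the healthcare objective. The documents do not support that. Section 2.0 states the objective as two pairwise comparisons, and the sentence on specificity to TJM sits in the primary-aim paragraph on pain and disability. What stands is narrower: those two comparisons are distorted if the interaction is left out.
- **6-month NDI and NPRS.** A reader might infer that the planned test is wrong. It is not: section 7.0 already names the three-way interaction, and both outcomes have a baseline. Only the hypothesis sentence is at fault.
- **Error rates.** One could fill baseline GROC with zeros, or assume additive effects at 6 months, and compute rejection rates. Neither scenario is in the plan, so such figures do not bear on how serious the point is.
- **FABQ.** A reader might extend the GROC fault to FABQ. FABQ has a baseline and its model can be fitted. Appendix C also says: "Also note that there is no total score where each subscale score is added as each subscale exists as a separate entity".

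**Conclusion.** Three statements in section 7.0 are wrong as written and should be corrected before outcome data are examined.

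1. The GROC three-way term cannot be estimated from the scheduled data (rank 4 of 8). The consequence is limited because the intended model is probably recoverable.
2. The optional visits interaction matters most. If it is omitted and only CPR+/TJM truly differs, each comparison in the secondary objective is estimated at half its true size, and a spurious rule-status difference of the same size appears in the MoE arm. This assumes equal cells.
3. The Secondary Aim #1 comparator contradicts section 2.0 and says nothing about the interaction. For visits this compounds item 2. For 6-month NDI and NPRS it is a fault of wording only.

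The fault is confined to secondary aims; the primary aim and the 31-per-cell calculation are untouched. The power figures assume equal variances and a normal approximation. They are in SD units because the plan gives no SD for GROC or visits.

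**What to change.** - **GROC.** Analyse the 6-month rating with treatment, CPR status and treatment by CPR; test treatment by CPR; use no time factor or baseline level. Keep the baseline-to-6-month model for FABQ.
- **Visits.** Delete the conditional wording and always include treatment by CPR. Estimate the two section 2.0 contrasts from the four-cell model. Report the interaction as the test of whether any rule-status difference is specific to TJM.
- **Hypothesis sentences.** In both Secondary Aim #1 sentences, replace CPR−/MoE with CPR+/TJM vs CPR−/TJM and CPR+/TJM vs CPR+/MoE, read alongside the interaction test.
- **Minor clarifications.** Reconcile the Secondary Aim #2 hypothesis, which expects "greater reduction in pain and fear avoidance beliefs than patients who are negative on the rule and received TJM", with that aim's modelled outcomes, by cross-reference to the 6-month NPRS model under Secondary Aim #1. State that each FABQ subscale has its own model. List the planned pairs and the number that Bonferroni divides by.

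The cost is wording in section 7.0, with no change to data collection or sample size. The downside is power: the interaction detects only about 0.95 SD at 80% power, so a non-significant result should not be read as evidence that the rule is not specific to TJM.

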# 4. Intention-to-treat analysis

The study will use an intention-to-treat analysis, where all participants are analyzed in the group to which they were originally assigned, regardless of whether they completed the treatment as planned. This approach helps to avoid bias introduced by dropout or non-

compliance, ensuring that the results reflect the effectiveness of the interventions under typical clinical conditions.

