# Treatment Session #2

The second treatment session will occur 2-4 days after the first session. Prior to beginning treatment session #2, all patients will complete the patient GROC to determine whether they experienced a clinically meaningful improvement.

Interventions provided for treatment session #2 will be identical to treatment session #1 consisting of three components: 1) Low grade cervical NTM, 2) a general mobility exercise (three-finger cervical rotation exercise), and 3) advice to maintain usual activity within the limits of pain.

# Treatment Sessions #3, 4, and 5

To ensure equal comparison and attention effect, the treatment administered in treatment sessions #3, #4 and 5, will be conducted according to the same protocol as the MTE group. The treatment program consists of three components: 1) warm-up exercises for 10 minutes, 2) a program of stretching and strengthening exercises for the cervical, thoracic and shoulder complex, and 3) advice to return to usual physical, work and recreational activity.

The third and subsequent treatment sessions will occur within 5-7 days of each previous treatment session. At each of these treatment sessions, patients will complete a GROC based on their perceived recovery since the baseline examination. As well as the GROC, all patients will complete a follow up NPRS, FABQ and NDI at the beginning of visits #3 and #5.

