# Stretching and Strengthening Exercises:

Patients/ therapists will be allowed to choose from the exercises depicted in Figure 4. They must choose at least 5 exercises from each of the 2 groups and perform exercises for a total time of 30 minutes.

If a participant terminates their involvement early, the results from their last appointment will be carried forward within the intention-to-treat analysis. The participant may pursue any and all healthcare treatment they would like upon termination or completion of the treatment portion (visits 1-5) of the study.

			-						
	Prior to	Visit	Visit 2	Visit 3	Visit	Visit 5	1 month	3-month	6-month
	Visit 1	1		(1 week)	4		follow-up	follow-up	follow-up
Treatment		Х	Х	Х	Х	Х			
Pre-Screen	Х								
Eligibility		Х							
Screening									
Medical		Х							
History									
Baseline		Х							
Assessment									
Demographics		Х							
Pain Diagram		Х		Х			Х	Х	Х
NDI		Х		Х			Х	Х	Х
NPRS		Х		Х			Х	Х	Х
GROC			Х	Х	Х	Х	Х	Х	Х
FABQ		Х		Х			Х	Х	Х

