# Data Analysis:

Descriptive statistics, including frequency counts for categorical variables and measures of central tendency and dispersion for continuous variables will be calculated to summarize the data. Baseline demographic data will be compared across treatment groups. The investigators will compare baseline variables between groups by using independent t-tests or Mann–Whitney U tests for continuous data and chi-square tests of independence for categorical data. If analysis of baseline data suggests randomization did not reasonably control for potential confounders, those covariates will be included in models to adjust for confounding variables. If appropriate, statistical adjustments will be made for baseline characteristics that are significantly different between groups. An intention-to-treat analysis will be utilized, in which all participants will be analyzed in the group to which they were originally assigned. All drop-outs and the reason for dropping out of the study will be reported. An *a priori* alpha level of 0.05 will be used for all analyses. All data will be screened to ensure they meet the assumptions for the inferential statistical analyses described below. If they do not meet the necessary assumptions, appropriate nonparametric procedures will be utilized.

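### No analysis that departs from missing at random is specified, and the imputation plan conflicts with a carry-forward rule elsewhere in the protocol

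*Combined protocol and SAP*

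**What the plan says.** Section 7.0 (Data Analysis, Primary Aim #1) analyses NPRS and NDI with "separate random intercept linear mixed models with treatment group (MTE vs. MoE), status on the CPR (positive or negative) and time" at baseline, 1 week and 4 weeks as fixed effects. The Missing Data paragraph notes that "analysis using mixed models allows all observed data to be included in the analysis under the assumption that the data are missing at random". It then provides that "if substantial missing data occurs, multiple imputation or mean conditional imputation will be used with subsequent sensitivity analyses to explore the impact of imputation", and that "bootstrapping procedures will be used on the entire imputation and estimation process". It gives no threshold for substantial, no variables or assumption for the imputation model, and no content for the sensitivity analyses. On dropout itself, Section 7.0 says "All drop-outs and the reason for dropping out of the study will be reported" and links those reasons to no analysis.

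Section 5.0 (MoE Group, Stretching and Strengthening Exercises) holds a second rule: "If a participant terminates their involvement early, the results from their last appointment will be carried forward within the intention-to-treat analysis". Section 7.0 does not mention it.

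Section 4.0, item 4, credits analysis by assigned group with helping against dropout bias.

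**The concern.** Analysing patients as assigned does not by itself remove bias when their outcomes are missing. What protects the estimate is the missingness assumption, and no section plans a defined departure from it. The bootstrap deals with the standard error only.

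Outcome-related dropout is plausible on the protocol's own facts. Section 4.0, item 2, lists assessors, treating therapists (as to CPR status) and the baseline examiner as blinded, but not participants. NDI and NPRS are self-reported. Positive expectation of manipulation is one of the four CPR criteria, so the CPR-positive block is likely to be enriched for patients who expect it, and half of that block receives low-grade mobilization. Someone who is not improving has a reason to leave before the 1-week questionnaire.

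At stake is what the report can claim. Agreement between the mixed model and a standard imputation could be read as robustness while a shared bias remains. With two missing-data rules in force, an analyst could also choose between different estimates after seeing the data.

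**Working it through.** **1. The plan's own figure.** Inputs from Sample Size and Power (Section 7.0): difference 10 NDI points, SD of change 12, two-sided alpha 0.05, power 90%. n per cell = 2 × (1.960 + 1.282)² × (12/10)² = 30.3, so 31. This reproduces. Four cells need 124. Recruiting 140 (35 per cell) leaves 16/140 = 11.4%, or 4 per cell. That margin also covers uneven CPR classification, so it is not a stated dropout rate.

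**2. What carry-forward means at 1 week.** The schedule table in Section 5.0 and Appendix G collect NDI at visit 1 and next at visit 3; visit 2 collects GROC only. A patient lost before visit 3 therefore has only the baseline NDI to carry, that is, zero change. The mixed model instead uses that patient's baseline under missing at random. The two rules treat the same patient differently.

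**3. Size by arithmetic.** Shift in a cell mean ≈ fraction lost × mean departure of the lost patients from what the model predicts for them.
- 4/35 × 12.5 = 1.4 points
- 11.4% lost, departure 5 to 12: 0.57 to 1.37 points
- 20% lost, departure 5 to 12: 1.0 to 2.4 points

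For scale, the standard error of a two-cell contrast is 12 × √(2/35) = 2.9 points.

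**4. Does imputation from the same variables reveal the bias?** Two simulations used 35 per cell, SD of change 12 and a true effect of −10. The dropout mechanisms are assumptions, not taken from the documents.

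*Scenario A:* three-way interaction at 1 week, random-intercept model, 120 replicates. The worst responders leave the CPR-positive MTE cell; loss elsewhere is equal and random. Imputation is from baseline within cell.

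| Loss | Full data | Mixed model | Standard imputation | Carry-forward | Imputation, that cell worsened by 10 |
|---|---|---|---|---|---|
| 11.4% | −9.46 | −11.52 | −11.60 | −10.71 | −10.46 |
| 20% | −9.83 | −12.77 | −13.02 | −10.87 | −11.02 |

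*Scenario B:* CPR-positive TJM versus NTM contrast, regression on baseline, 2,000 replicates. Poor responders leave the NTM cell only.

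| Loss in NTM cell | Full data | Regression under missing at random | Standard imputation | Carry-forward |
|---|---|---|---|---|
| 11% | −10.07 | −8.37 | −8.37 | −8.56 |
| 21% | −9.91 | −7.11 | −7.10 | −7.73 |
| 24% | −9.95 | −6.21 | −6.22 | not run |

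In A, imputation differs from the mixed model by 0.08 and 0.25 points on average, while both overstate the effect by about 2.1 (11.52 − 9.46) and 2.9 (12.77 − 9.83). In B the two differ by at most 0.01, while both understate it by 1.7, 2.8 and 3.7. Carry-forward gives a third answer and is still biased. In B at 11% loss, worsening the imputed values by 10 points brings the estimate to −9.52.

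**The case against.** The strongest reply is that the text is silent rather than wrong. Missing at random is attached to the mixed model only; that the imputation shares it is an inference from normal practice. The sensitivity analyses follow imputation and are undefined, so they could in principle include something more searching. This stands, and it limits the criticism to what has been specified.

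Near-equality of the two estimates also needs the same variables in both. GROC is collected before session 2, ahead of the 1-week NDI, and is not in the NDI model. A simulation with 24% loss in one cell added an early-response variable, with assumed correlation 0.3 to 0.7 with the 1-week residual. When dropout depended on the unseen outcome, imputation moved from −7.0 to between −7.25 and −8.42. When dropout depended on the observed early response, the unimputed estimate was −9.1 to −7.9 and imputation recovered about −10.0. A reader might infer that comparing imputed with unimputed results can never be informative; that does not hold. But the plan does not say that GROC will be used, a patient who leaves before session 2 has none, and in the first case most of the bias remained.

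Finally, the sizes are chosen. Heavy loss in a single cell within a week appears nowhere in the documents, retention incentives are planned, and 1.4 points is about half the standard error of a two-cell contrast. This stands as a limit on magnitude. It does not supply the missing analysis, nor does it reconcile the two rules.

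**Conclusion.** The point holds in this form. The named imputation work, by default, shares the mixed model's assumption and is not designed to show whether loss of poor responders changes the conclusion; and Sections 5.0 and 7.0 give two unreconciled rules for early leavers. The conflict is provable from the text. The default assumption of the imputation is a reasonable inference.

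Three stronger readings are tempting and not supported. That the plan's sensitivity work is incapable of detecting informative dropout: its content is unspecified. That a bias of 2 to 4 points should be expected: those figures rest on assumed mechanisms and loss rates. That 11.4% is the planned dropout: the margin has two purposes and no rate is given. Nor can the bias be assumed conservative, since scenario A inflates the effect and scenario B shrinks it. A fair illustrative size is about 0.6 to 1.4 NDI points in one cell at 4 of 35 lost, for departures of 5 to 12.5 points.

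**What to change.** 1. State one primary rule in Section 7.0: the mixed model on all observed data under missing at random. Delete the carry-forward sentence in Section 5.0, or relabel it as a sensitivity analysis and say that at 1 week it carries the baseline NDI.
2. Replace the imputation sentence with a delta-adjusted (tipping-point) multiple imputation of 1-week NDI, run whatever the amount of missing data. Include early GROC as an auxiliary variable where it was collected. Worsen imputed values over a prespecified range, for example 0 to 10 points, separately in each treatment-by-CPR cell, and report the shift at which the primary conclusion changes. The range is a choice for the investigators to justify; state it on the same NDI scale as the sample-size figures.

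The cost is SAP wording plus a small amount of extra programming and reporting, largely in place of imputation work already planned. It requires no new data collection and no change to sample size, and should be settled before outcome data by group are seen.
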